Effect on Airflow of a Vibrating Mesh Nebulizer Compared to a Jet Nebulizer for Delivery of Bronchodilator Therapy to Acute Severe Asthma Patients in an Emergency Department

NCT03029156

Version Date: June 20, 2016

Version date: **06/20/2016**

Principal Investigator: [name]

Study Title: Effectiveness of the Aeroneb Compared to a Jet Nebulizer for the Delivery of Bronchodilator Therapy of Acute Severe Asthma

I. Aim and Hypotheses

Acute exacerbations of asthma remain a frequent cause of emergency department (ED) visits and hospital admissions. About one-fifth to one-third of ED patients have poor short term responses to bronchodilator therapy and require admission to the hospital. The initial response to bronchodilator is an important indicator of favorable outcomes. The response to bronchodilator therapy is determined by patient-specific factors but it is also possible that the delivery method of bronchodilator therapy could be playing a role in the response to bronchodilator. Aeroneb system utilizes vibrating mesh technology to generate consistently sized particles with greater lung deposition. It may provide greater benefits in acute asthma exacerbations.

Aim: To study whether Aeroneb nebulizer is more effective than small volume jet nebulizer in delivering bronchodilators in severe asthma exacerbation

Hypothesis: Compared to small volume jet nebulizer, the Aeroneb nebulizer is more effective than a small volume jet nebulizer for delivering bronchodilator therapy in patients with acute severe asthma.

We hypothesize that the mean of PEFR percentage of predicted at 30 minutes after the initial bronchodilator treatment in the Aeroneb group will be 10 points higher than the mean of PEFR percentage of predicted at 30 minutes after the initial bronchodilator treatment in the small volume jet nebulizer group.

II. Background and Rationale

A. Background:

Acute exacerbations of asthma remain a frequent cause of emergency department (ED) visits and hospital admissions. About one-fifth to one-third of ED patients have poor short term responses to bronchodilator therapy and require admission to the hospital¹. The presence of peak expiratory flow rate (PEFR) < 40% is an indicator of severe asthma². In patients with peak flow <50% **severe asthma**, the improvement in PEFR at 30 minutes after the initial bronchodilator treatment is associated with favorable outcomes³. Initial response to bronchodilators may be affected by patient-specific factors such as duration of symptoms and frequency of beta agonist use prior to ED admission. It is also possible that the method of delivering bronchodilator therapy in the ED impacts outcome.

The effectiveness of aerosol delivery systems in this clinical setting depends upon the capacity to generate particles that reach the small airways of the lower respiratory tract, which is the site of disease in acute asthma. Jet nebulizers, which are often used in the ED treatment of asthma, are inexpensive systems that deliver aerosols of varying particle size and have been shown to be unreliable in delivering the bronchodilator drugs⁴. Vibrating mesh technology, which is employed in the Aeroneb system, produces consistently sized respirable particles of 3.4 μm mass mean aerodynamic diameter⁵. This improvement in aerosol delivery technology translates into greater lung particle deposition in both animal studies and in normal humans⁷. Therefore, the Aeroneb nebulizer may be more effective than small volume jet nebulizer in the management of asthma exacerbations.

The Aeroneb Nebulizer System is a portable medical device for single patient use that is intended to aerosolize physician-prescribed solutions for inhalation to patients on and off ventilation.

The Aeroneb Adapter is an accessory specific to the Aeroneb Nebulizer. It facilitates intermittent and

continuous nebulization and optional supply of supplemental oxygen to adult patients in hospital use environments via a mouthpiece or aerosol mask. The Aeroneb Nebulizer System and Adapter are FDA approved devices for nebulizing solutions including bronchodilators (albuterol and ipratropium).

B. Rationale:

Aeroneb system has advantages over the small volume nebulizer as mentioned above. These advantages may make it more efficient system to deliver the bronchodilator therapy and to treat the asthma exacerbations more effectively.

This is the first study that we are aware of that will look at the use of Aeroneb system to deliver bronchodilator therapy in asthma exacerbations.

The study will provide novel data to demonstrate whether the use of Aeroneb system to deliver bronchodilator therapy is advantageous to patients with severe asthma exacerbations.

If the hypothesis is proven to be correct this will mean improved patient's outcomes in severe asthma exacerbations and potentially shorter ER stay, reduction in the hospitalization rate and cost of care.

III. Research Plan

A. Experimental design:

This is a prospective, single blinded, parallel, single center, randomized controlled clinical trial (n=68). Upon entry into the study, patients will be randomized to two groups:

Treatment group: All the bronchodilator therapies during the ER visit (albuterol and ipratropium) will be delivered via Aeroneb nebulizer system. The asthma management will be as per the adult asthma protocol in the ER.

Control group: All the bronchodilator therapies (Albuterol and ipratropium) will be delivered via small volume jet nebulizer system, which is currently the standard nebulizer device used in the emergency department at Tufts Medical Center. The asthma management will be as per the adult asthma protocol in the ER.

B. Sample size and statistical analysis(es):

Upon entry into the study patients will be randomized at a 1:1 ratio with permuted block design of 6 to one of the 2 groups. Randomization will be conducted using a computerized randomization scheme and secured in a sealed envelope for allocation.

For a power calculation to determine the sample size, historical data was utilized from prior clinical study that examined the effect of bronchodilator (B2-agonist) treatment on the improvement of the peak flow measurement after 30 minutes of the initial bronchodilator treatment⁴. In this study, the mean PEFR improved from 27% to 39% at 30 minutes after the initial bronchodilator treatment. We hypothesize that mean PEFR of the intervention group at 30 minutes of the bronchodilator therapy will be at least 10 points higher than the control group (i.e. mean PEFR \geq 49% at 30 minutes of the initial bronchodilator therapy). Group sample sizes of 34 and 34 is required to achieve a power $> 80\%$ to reject the null hypothesis of equal means when the groups mean difference is 10.0 with a standard deviation for both groups of 14.4 and with a significance level (alpha) of 0.050 using a two-sided two-sample equal-variance t-test.

Taking into consideration the screen failures the disqualification and drop-outs, we are anticipating enrolling around 110 patients in order to have 68 patients who will complete the study objectives.

For the statistical analysis treatment evaluations will be performed on the principle of intention to treat (ITT) using the data collected from all randomized participants who completed the study procedures including the two parts of the informed consent form (ICF). Demographics and baseline characteristics of patients will be summarized for each group. Continuous variables will be reported as mean \pm standard deviation, with minimum, median, and maximum values.

Categorical variables will be reported as n and %. All statistical testing will be two-sided with alpha=0.05.

For the primary outcome, mean PEFR at 30 minutes post-bronchodilator treatment, analysis of covariance (ANCOVA) with adjustment for baseline PEFR will be utilized.

ANCOVAs with adjustment for baseline values, and incorporating repeated measures where appropriate, will be utilized for the following secondary outcomes: absolute value of PEFR (L/Min) at 30 minutes, PEFR percentage of predicted at 60 minutes and 180 minutes, FEV1 percentage of predicted as well as absolute FEV1 (L/Sec) at 30 minutes, 60 minutes and 180 minutes, Borg dyspnea score at 30 minutes, 60 minutes and 180 minutes, accessory muscle use score at 30 minutes, 60 minutes and 180 minutes, and heart rate at 30 minutes, 60 minutes and 180 minutes.

The outcomes which are measured at different time points will be averaged for each group and plotted to visualize the trajectory of those outcomes.

Differences in length of stay (hours) in the ER and the total doses of albuterol and ipratropium will be compared using T-tests or non-parametric methods (e.g., Mann-Whitney test) as depending on the distribution of the data. The proportion of patients in each group who require hospitalization will be compared using a Chi-square test.

C. Subject Characteristics

1. Subject criteria:

The study will be conducted at the emergency department at Tufts Medical Center.

a) Inclusion criteria:

- Acute asthma exacerbations presenting to the emergency room
- Peak expiratory flow rate at presentation <50%40% of predicted
- Enrolment within 90 minutes of the arrival to the ER
- Age 18-55 years old

b) Exclusion criteria:

- History of chronic obstructive pulmonary disease
- Clinical evidence to suggest a non-asthmatic cause of bronchospasm as determined by the treating physician
- Clinical evidence of acute coronary syndrome
- Respiratory failure requiring mechanical ventilation either invasive or non-invasive
- Tachyarrhythmia other than sinus
- Agitated or uncooperative
- Inability to provide informed consent

c) Withdrawal/Termination criteria:

The subject will be withdrawn from the study if any of the following:

- The subject develops respiratory failure requiring mechanical ventilation (invasive or non-invasive)
- The subject becomes unable to perform peak flow measurement at the pre-specified time points
- The treating physician determines that it is not clinically advisable to continue with the study.
- The subject opts to decline to sign the second part of the informed consent form. In this case, the data collected may not be used for the study.

A study participant will have the right to withdraw from the study at any point of the study.

A study participant may not participate in another research study while participating in this study.

D. Risk/benefit assessment:

1. Physical risk:

Patients in both the intervention and control arms are at risk for developing respiratory failure as a result of severe asthma exacerbation and it is unknown if the risk of such complications is higher in any arm. It is possible that the Aeroneb group patient may experience more frequent side effects related to potentially more albuterol and ipratropium delivery and those side effects may include tremor and arrhythmias.

2. Psychological risk:

There is no increased psychological risk to the study participants from the study for either arm

3. Social risk:

There is no increased social risk to the study participants from the study for either arm

4. Economic risk

There is no increased economic risk to the study participants from the study for either arm.

5. Benefit of participating in the study:

- a) Patients randomized to the intervention group may benefit from the increased bronchodilator delivery by Aeroneb system
- b) Future asthma patients may benefit from this study if Aeroneb system is proven to be more effective in treating severe asthma exacerbation

E. Specific methods and techniques used throughout the study:

1. Laboratory tests:

No additional laboratory test is required in the study.

2. Study Procedures:

-The patient presenting with acute severe asthma exacerbations to the emergency room will be screened by the PI, co-investigator or research coordinator to determine their eligibility based on the inclusion and exclusion criteria.

-The required treatment must not be delayed for a research related reason and patients will still be eligible for enrollment after receiving the treatment as long as their PEFR<50%40% of predicted and the enrollment occur within 90 minutes of the ER arrival time.

- The initial part of the consenting process will cover the essential elements of the informed consent in a concise manner to ensure timely process

-Eligible patient will be randomized using the method mentioned above to either the intervention arm or the control arm. The randomization should take place within 90 minutes of the ER arrival, however, every effort will be made to enroll the patient as soon as possible; patients will be enrolled as long as their PEFR is less than 50% 40% of predicted regardless of the number of bronchodilator treatment they received prior to the randomization.

-The assignment will be blinded to the recording investigator and the treating physician but not to the patient or the nurse or respiratory therapist who is administering the nebulization. In order to avoid any delay in administering the treatments, the sets of Aeroneb nebulizer and small volume jet nebulizer will be stored in identical boxes and will be readily available in the ER.

In order to blind the treating physician and the recording investigator, a sign "treatment in progress" will be displayed at the outdoor of the ER room when the patient is getting the bronchodilator treatment. The nebulizer devices will be placed in the box between the bronchodilator treatment sessions. The physician and the recording investigator will be asked if possible to see the patients only when the sign is taken off the outdoor.

-Once assigned, all the bronchodilator treatments in the ER will be administered using the nebulizer device assigned to that patient.

-The Peak flow and FEV1 will be measured using Spirometer (micro I). Both values will be obtained through the same exhalation maneuver.

-Patient will be treated and managed according to the asthma ER adult protocol or as directed by the ER physician who is in charge of patient's care

-After the study procedures have been performed and the subject is determined to be in stable condition and have the capacity to make medical decisions, the investigator will approach the subject again and review all the elements of the ICF again with the subject. The collected data will be used only if the subject signs both parts of the informed consent.

-Within two weeks of the subject participation, the research team will attempt to conduct a phone interview with the subject to obtain their feedback on the study procedures and mainly on the informed consent process. The phone interview questionnaire is included in the supplement

-The research team will report to the IRB the progress of the study including the consent process after enrolling the first 10 patients.

3. Subject Timeline:

During the study several data will be recorded, most of them are standard hospital recording, which are conducted frequently. These data will be collected at baseline and at multiple points after the initial bronchodilator therapy (at 30 ± 10 minutes, 60 ± 10 minutes, at 180 ± 10 minutes and upon disposition from the ER). All recorded data are obtained through noninvasive measurements. No samples of any body component will be taken that is not part of the normal standard hospital protocols.

The results that will be collected are summarized in table 1.

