We do not anticipate serious complications attributable to the device, but will monitor patients for potential adverse effects such as discomfort or cough. Any serious adverse events that occur during use are more likely due to the underlying disease than the device itself, but will be reported promptly to the IRB by the investigators per the reporting timeframes described above.

The Research team will report to the IRB the process of the informed consent after enrolling 10 patients (if this occurs before the study continuing review).

G. Subject Participation

1. Recruitment:

Patients presenting with severe asthma exacerbation to Tufts Emergency Room will be recruited on to the study. Patients who meet any exclusion criteria will not be screened for possible enrollment. Patients will be approached at their bedside by the PI, co-investigator or research coordinator. No advertisements will be used.

2. Registration:

Patients, that can potentially take part in the study, will be assessed by the PI or the co-investigator for their ability to fulfill the eligibility criteria and meet the exclusion criteria, as listed above.

3. Screening Interview/questionnaire: Not applicable

4. Transportation: Not applicable

5. Informed consent process and timing of obtaining of consent:

The participant must have the full mental capacity to provide the consent. The consenting process will be two steps process, each step will involve face-to-face meeting with one of the study investigators at bedside in the ER room

1-The first part of the consent will cover all the essential elements of the informed consent. Given the acuity of the medical condition, it is anticipated that the total amount of time given to this step of the informed consent will be no longer than 10 minutes. No study related procedures will be conducted until this step of the informed consent is signed off by the subject. Permission will also be obtained from the primary provider for the participation of the patient in the study before a discussion with the patient regarding consent occurs.

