The PI, co-investigator or the research coordinator will oversee the study procedure. Normal clinical care of patients will be performed by the patient's assigned nurse, respiratory therapist and doctor in the emergency room.

b. Primary responsibility for the following activities:

i. Obtaining informed consent:

The principal investigator and the co-investigators will be responsible for obtaining the informed consent from the patients.

ii. Providing on-going information to the study sponsor and the IRB:

[name] and [name] will be responsible for providing on-going information to the study sponsor and the IRB.

iii. Maintaining participant's research records:

[name] will be responsible for maintaining the participant's research records. The records will be maintained up to 7 years as per the IRB policy.

8. Subject fees:

There will be no fees paid to subjects for the study. It is part of their emergency visit care treatment

9. Study results:

Study results will not be given to patients.

10. Procedures to protect subject confidentiality:

Patient confidentiality will be maintained under normal emergency room procedures which are in compliance with the HIPPA rules.

11. Confidentiality:

a. Certificate of Confidentiality:

Certificate of confidentiality is not relevant for this research study

b. How data will be coded, recorded, and stored to protect confidentiality:

Study participants will be allocated a study number, which will be used as a study identifier on all study forms. The study data and records will be kept locked.

c. Parties who will have access to the date, including the key to the identity code:

The study PI, [name] and research team member [name] will have access to the study data and the identity codes.

d. Parties who will have access to research records:

The study PI, [name] and research team member [name] will have access to the study data.

12. Collaboration:

This is not a collaborative study.

13. Alternatives:

Patients not participating in this study will receive usual ER care as determined by the ER.

14. How new information will be conveyed to the study subject and how it will be documented:

In the event new information is discovered about the study, a letter describing the new information will be mailed to the contact address for each subject who participated in the study.

15. Payment, including a prorated plan for payment:

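### A fixed block size of 6, printed in the protocol of a single-centre open-device trial, would make up to a quarter of assignments certain to anyone who knows the earlier ones, and the protocol does not keep recruiters from knowing them

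*Combined protocol and SAP*

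**What the plan says.** Section III.B gives the whole of the allocation method. Patients are "randomized at a 1:1 ratio with permuted block design of 6 to one of the 2 groups", and "Randomization will be conducted using a computerized randomization scheme and secured in a sealed envelope for allocation". No stratification is mentioned, and neither is any change in block size. The section does not say whether the envelopes are opaque or numbered, who keeps them, who opens them, or when.

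On blinding, section III.E.2 states: "The assignment will be blinded to the recording investigator and the treating physician but not to the patient or the nurse or respiratory therapist" giving the treatment. The two device sets are stored in identical boxes, and the device goes back into its box between treatments. A sign on the door shows when a treatment is running, and the physician and recording investigator "will be asked if possible to see the patients only when the sign is taken off the outdoor".

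On recruitment, section III.E.2 gives screening to the principal investigator, co-investigator or coordinator. Section III.G.1 adds: "Patients will be approached at their bedside by the PI, co-investigator or research coordinator". Section III.G.7 then says: "The PI, co-investigator or the research coordinator will oversee the study procedure". Section III.G.5 requires the primary provider's permission before consent is discussed, and no study procedure may take place before the first part of the consent is signed.

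**The concern.** Blinding the person who records PEFR protects the measurement. It does not protect the choice of whom to enrol, which lies with whoever screens and approaches. That choice leaves room for judgement: enrolment may fall anywhere in a 90-minute window, any number of earlier bronchodilator treatments is allowed, agitated or uncooperative patients are excluded, and the investigator may end a consent discussion.

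If a recruiter knows or suspects the next device, patients may be approached sooner, later or not at all, without any intention to bias the trial. The groups can then differ in prognosis. The primary ANCOVA adjusts for baseline PEFR only, so it removes the part of such a difference that PEFR carries. Section II.A itself names symptom duration and prior beta-agonist use as possible influences on the response. An imbalance in these would be only partly removed.

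**Working it through.** **Plan's own figure.** Inputs from section III.B: difference 10.0 points, SD 14.4, two-sided alpha 0.05, equal-variance t-test. The noncentral t calculation needs 33.5, so 34 per group, with power 80.5% at 34 per group. The stated sample size is reproduced. The documents give no figure for predictability.

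**Certain assignments in a block of 6.** Inputs: block size 6 and ratio 1:1 (section III.B), so m = 3 per arm and 20 equally likely orders. An assignment is certain once one arm's three places are used up.

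| Position | 1 | 2 | 3 | 4 | 5 | 6 |
|---|---|---|---|---|---|---|
| Chance that it is certain | 0 | 0 | 0 | 0.1 | 0.4 | 1.0 |
| Chance that the best guess is right | 0.5 | 0.6 | 0.6 | 0.7 | 0.7 | 1.0 |

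- Certain: 0.1 + 0.4 + 1.0 = 1.5 per block. The closed form 2m/(m + 1) = 6/4 = 1.5 agrees. 1.5/6 = 25%.
- Best guess (name the arm that is behind): 0.5 + 0.6 + 0.6 + 0.7 + 0.7 + 1.0 = 4.1 per block. 4.1/6 = 68.3%, against 50% by chance.

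**Over the trial.** Section III.B wants 68 completers from about 110 enrolled, a figure that includes screen failures, so the number randomised lies between 68 and 110.

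- 68 randomised = 11 full blocks + 2: 11 × 1.5 = 16.5 certain, 24.3%.
- 110 randomised = 18 full blocks + 2: 18 × 1.5 = 27 certain, 24.5%.

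**Incomplete knowledge.** An assignment is certain only if all three earlier patients in the used-up arm are known. Suppose that each past assignment is known independently with probability p (an assumption; the documents give no value). The certain share is then 25% × p³: 25% at p = 1, 12.8% at p = 0.8, 3.1% at p = 0.5.

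**Mixed blocks.** Simulation of 68 patients, with sizes drawn at random from 4, 6 and 8. The observer knows the set of sizes and every past assignment, but not the order of sizes. Certain assignments: about 2.3% to 2.5% across separate runs. Best-guess accuracy: about 68%. Fixed blocks of 6 over the same 68 patients give 24% and 68%.

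**Balance and power after the change.** If 68 are randomised, a largest block of 8 can be cut off at four to nil, so the worst split is 36/32. Fixed blocks of 6 can already end at 35/33 (33 + 2 against 33). Power is 80.5% at 34/34 and 80.4% at 36/32.

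**The case against.** A reader might infer that a quarter of assignments are in fact predictable to the staff who choose whom to enrol. The documents do not support that. The roles named as unblinded are the patient, nurse and respiratory therapist, and none has a stated part in selecting patients. No section says that recruiters know past assignments, or that all staff know the block size. That the size is known is an inference from its being printed in the protocol. Overseeing the procedure need not mean seeing the device. If the recruiter is also the recording investigator, the blind is meant to cover that person.

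There are real safeguards too: the computer list, the sealed envelope, the identical boxes, the return of the device between treatments, consent before any study procedure, and permission from a provider. If that provider is the treating physician, this person is also to be blinded. The words about possibility qualify only the request to stay out of the room, not the intention to blind.

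All of this stands, and it makes 25% a ceiling. It does not close the gap. The blind names two roles, and recruiters as such are not among them. It rests on a door sign and a request. The nurse and therapist, who know the device, are a possible route by which recruiters could learn past assignments.

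A second objection also stands: varying the block size alone leaves guessing almost unchanged, so it removes certainty but not suspicion.

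**Conclusion.** The concern holds as an avoidable weakness in the allocation method. With blocks fixed at 6, up to about 25% of assignments (about 16.5 of 68) would be certain, and 68% guessable, for an observer who knows the block size, the block starts and all earlier assignments. The share falls quickly with incomplete knowledge, to about 3% if half of past assignments are known independently.

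The documents do not show that any recruiter will have this knowledge. They show that nothing is planned to prevent it, in a single-centre trial whose recruiting roles also oversee the procedure. No bias in 30-minute PEFR can be estimated from the documents, and none is claimed. The sample size is unaffected. The change is worth making because it costs almost nothing and because analysis cannot fully repair selection bias afterwards.

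**What to change.** - Generate the list with block sizes varied at random, for example 4, 6 and 8. In the protocol, say only that permuted blocks of varying size are used, and keep the sizes in a restricted document that recruiters do not hold.
- State that those who screen, approach and consent are not told past assignments. Keep the opened envelopes and the allocation log away from them, and separate oversight of nebulisation from recruitment where staffing allows. This step matters most, because mixed blocks leave best-guess accuracy near 68%.
- State that envelopes are opaque and sequentially numbered. Have the nurse or respiratory therapist, who is already unblinded, open the next one only after the first part of the consent is signed and baseline PEFR is recorded.

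Cost: one regenerated list, one restricted document, a few sentences in sections III.B and III.E.2, and an instruction to the nurses and therapists. The downside is a final split of up to 36/32 if 68 are randomised, with power 80.4% instead of 80.5%.
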